**Figure 1: Study Design**

\*All subjects during the Run-in period must be willing to comply with usage of iNOpulse device for  $\geq 12$  hours (rounded to the nearest hour) per day, with no more than 2 days of usage  $< 8$  hours per day. Subjects randomized to iNO will receive 15 mcg/kg IBW/hr for the first 2 weeks (Run-in phase) followed by iNO at 75 mcg/kg IBW/hr dose for the Treatment Period. Subjects randomized to Placebo will receive Placebo product 15 mcg/kg IBW/hr at a delivery setting matching the treatment groups.

Additional details regarding assessments done at each visit can be found in section 11.1 of CSP.

**Inclusion and Exclusion Criteria:**

There are a total of 11 inclusion criteria's and 26 exclusion criteria's for double blind period of study. They can be found in protocol deviation specifications.

**Inclusion Criteria:**

1. Signed Informed Consent Form prior to the initiation of any study mandated procedures or assessments.
2. A confirmed diagnosis of PAH Group 1 who have either idiopathic PAH (IPAH), heritable PAH, drug and toxin-induced PAH, associated PAH (APAH) with connective tissue disease (CTD), APAH with repaired simple congenital systemic to pulmonary shunt (i.e., atrial septal defect, ventricular septal defect and/or patent ductus arteriosus; complete repair at least 1 year prior to Screening), APAH with human immunodeficiency virus (HIV), or APAH with portal hypertension.
3. Subjects receiving at least one PAH specific therapy (ERA or PDE-5 inhibitor, or inhaled, subcutaneous, or intravenous prostacyclin or a prostacyclin analog) with the same type of therapy for at least 3 months with stable dosing 4 weeks prior to Screening. (Subjects should be receiving optimal therapy according to the disease severity).
4. Subjects using oxygen therapy by nasal cannula for at least 4 weeks prior to Screening.
5. PAH diagnosis confirmed by RHC within the previous 5 years, according to the following definitions:
  - $PVR \geq 400 \text{ dynes}\cdot\text{sec}\cdot\text{cm}^{-5}$  (5 Wood units)
  - $mPAP \geq 25 \text{ mmHg}$
  - $PCWP \text{ or } LVEDP \leq 15 \text{ mmHg}$
  - Subjects who otherwise meet all the inclusion criteria and none of the exclusion criteria but have not undergone a RHC within the previous 5 years may be considered eligible for the study if they undergo a RHC and then meet the pulmonary hemodynamics criterion.
6.  $6MWD \geq 100$  meters and  $\leq 450$  meters prior to randomization.
7. WHO Functional Class II-IV. Subjects with WHO Functional Class IV should be treated with prostacyclin or a prostacyclin analog (subcutaneous or intravenous), plus at least one PULSE-PAH-004 Phase 3 Protocol additional PAH specific therapy (ERA or PDE-5), if available to the subject and reimbursed by health insurance.
8. Age between 18 and 80 years (inclusive).
9. Willingness to use INOpulse delivery device for at least 12 hours per day.
10. Willingness to continue on study drug until the subject has completed Week 18 assessments.
11. Female subjects of childbearing potential must have a negative pre-treatment pregnancy test (serum or urine). All female subjects should take adequate precaution to avoid pregnancy.

**Exclusion Criteria:**

1. Subjects with known HIV infection who have a history within the past 3 months of any opportunistic pulmonary disease (e.g., tuberculosis, Pneumocystis carinii pneumonia, or other pneumonias) at the time of Screening.
2. PAH associated with, untreated thyroid disorders, glycogen storage disease, Gaucher's disease, hereditary hemorrhagic telangiectasia, hemoglobinopathies, myeloproliferative disorders or splenectomy.

3. Subjects with pulmonary conditions that may contribute to PAH including, but not limited to, chronic bronchiectasis, cystic fibrosis, or other pulmonary condition that the Investigator may deem to contribute to the severity of the disease or impair the delivery of iNO due to airway disease.
4. Subjects receiving riociguat.
5. Subjects receiving oral prostanoids as monotherapy.
6. <Exclusion deleted via Protocol Amendment #3>
7. PAH associated with significant venous or capillary involvement, known or suspected pulmonary veno-occlusive disease, or pulmonary capillary hemangiomatosis.
8. Any subject with WHO PH Groups 2, 3, 4 or 5
9. Subjects with any of the following cardiac abnormalities:
  - a. Underlying cardiomyopathy or clinically significant aortic or mitral valve disease in the opinion of the investigator
  - b. Left ventricular systolic dysfunction (LVSD), i.e., left ventricular ejection fraction (LVEF) < 40% or left ventricular shortening fraction (LVSF) < 22%, as determined by local reading
  - c. Current symptomatic coronary artery disease, myocardial infarction within 1 year, or any coronary artery interventions within 6 months.
10. Systemic hypertension defined as systolic blood pressure (SBP) > 160 mmHg and/or diastolic blood pressure (DBP) > 100 mmHg persistent at Screening after a period of rest (treated or untreated).
11. Subjects with a history of deep vein thrombosis, pulmonary embolism/infarction or prothrombotic disorder must have had chronic thromboembolic pulmonary hypertension (CTEPH) excluded by ventilation/perfusion lung (V/Q) scan.
12. Severe obstructive lung disease defined as both a forced expiratory volume in 1 second/forced vital capacity (FEV1/FVC) < 70% and FEV1 < 55% of predicted value.
13. Moderate to severe restrictive lung disease: total lung capacity (TLC) < 60% of predicted; if TLC 60% to 70% predicted, a high resolution CT scan showing diffuse disease or more than mild patchy disease
14. Any subject who develops or has developed a PCWP > 20 mmHg during acute vasodilator testing (AVT).
15. Systemic hypotension defined as SBP < 90 mmHg persistent at Screening after a period of rest.
16. Moderate to severe hepatic impairment, i.e., Child-Pugh Class B or C.
17. On dialysis.
18. Acute or chronic physical impairment (other than dyspnea due to PAH) that would limit the ability to comply with study procedures or adherence to therapy (i.e., 6MWT), including carrying and wearing the pulsed delivery device per study protocol, or medical problem(s) likely to preclude completion of the study.
19. Pregnant or breastfeeding females at Screening.
20. Administered L-arginine within 1 month prior to Screening.
21. Known concomitant life-threatening disease with a life expectancy less than 1 year.
22. Atrial septostomy within 3 months preceding randomization.

23. The concurrent use of the INOpulse device with a continuous positive airway pressure (CPAP), bilevel positive airway pressure BiPAP, or any other positive pressure device.
24. Use of investigational drugs or devices within 1 month prior to Screening (other than acute vasodilator testing with iNO).
25. Any underlying medical or psychiatric condition that, in the opinion of the Investigator, makes the subject an unsuitable candidate for the study.
26. Any subject who has been enrolled in any previous clinical study with inhaled NO administered through pulse delivery.

## 5.2 Visit Schedule

This study has several scheduled visits for part I & II (Table 17 and Table 18) as follows:

**Table 17: Visit Schedule – Part I**

Visit Name	Number	Duration	Target day	Window	Day Range
Screening	V0	NA	NA	NA	NA
Baseline	V1	NA	1	28 Days of Screening	≤ 1
Week 2	V2	Month 0.5	14	±3 Days	11-17
Week 6	V3	Month 1	42	±7 Days	35-49
Week 10	V4	Month 2	70	±7 Days	63-77
Week 14	V5	Month 3	98	±7 Days	90-105
Week 18 (End of blinded phase)	V6	Month 4	126	±7 Days	118-133

**Table 18: Visit Schedule – Part II**

Visit Name	Number	Duration	Target day	Window	Day Range
Week 0	V7	NA	126	±7 Days	118-133

Visit Name	Number	Duration	Target day	Window	Day Range
(week 18 of part I)					
Week 2	V8	Month 0.5 for Part II	140	±3 Days	137-143
Week 16	V9	Month 4 for Part II	238	±14 Days	224-252
Week 32	V10	Month 8 for part II	350	±14 Days	336-364
Every 4 months until EOS	V11 onwards	Every 4 months in Part II	NA	±14 Days	As appropriate

All efficacy analysis will follow above given study assessment window range.

Visit Window mapping for Safety as follows:

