- Pregnancy test
- Survival status
- All blinded drug cartridges from Part 1 of the study must be returned to the site or Sponsor.

Assessments Part 2

Part 2 Week 0 Visit: The following Assessments will be performed:

- Informed Consent
- Methemoglobin via pulse oximetry (O₂ flow rate)
- Drug Device Dispensation for Open Label treatment
 - If the subject continues to participate, at this visit the subject will be dispensed a 1 week supply of study drug. Additional supplies will be delivered directly to the subject's home every 4 weeks. The used cartridges must be returned and will be picked up from the subject's home when the new supplies are delivered.

- Pregnancy test (at the discretion of the investigator)
- Evaluation for symptomatic Rebound Hypertension while under medical supervision, after start of study drug and prior to sending the subject home as described in [section 11.1.15](#)

Part 2 Week 2 Visit is a Telephone Visit:

Study Staff will contact the subject via telephone call and the following assessments will be completed:

- Review of prior and concomitant medications
- Assessment of AE,SAEs, AESI

Part 2: Week 16, Week 32, and Week 52 Visits - the following assessments will be performed:

- Prior and concomitant medications
- WHO Functional Class
- Conduct 6 Minute Walk Test
- Borg Dyspnea Scale
- Laboratory – Hematology and Chemistry (Week 52 only)
- Pregnancy test (at the discretion of the Investigator)
- Vital Signs including HR, RR, BP and temperature. SpO₂ and methemoglobin (Week 52 only) via pulse oximetry (O₂ flow rate)
- Assess AEs, SAEs. AESIs
- Drug Device Dispensation (every 4 weeks via home delivery)
- Review Drug Device Usage
- Evaluation for symptomatic Rebound Hypertension while under medical supervision, after start of study drug and prior to sending the subject home as described in section 11.1.15

Part 2: Every 4 Month Visits: The following assessments will be performed:

- Prior and concomitant medications
- Assessment of AEs, SAEs, AESI
- Vital signs: BP and HR, SpO₂ and methemoglobin via pulse oximetry (annually)
- Review device usage with the subject
- Laboratory – Hematology and Chemistry will be conducted on a yearly basis (Pregnancy testing will be left to the discretion of the Investigator)
- Drug Device Dispensation (every 4 weeks via home delivery)

Part 2: End of Study (EOS) or Early Discontinuation- The following assessments will be performed:

- Prior and concomitant medications

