Assessment	Week 0 If subject enters Part 2, Week 0 assessments are done at Week 18 of Part 1	Week 2 +/- 3 days (phone call)	Week 16 Month 4 +/-14 days	Week 32 Month 8 +/-14 days	Week 52 Month 12 +/-14 days	Every 4 Months until EOS +/-14 days	EOS (or Early D/C	
Informed Consent	X ¹							
Inclusion/Exclusion Criteria	X ²							
Review of Prior and Concomitant Medications		X	X	X	X	X	X	
WHO Functional Class			X	X	X			
6 Minute Walk Test			X	X	X			
Borg Dyspnea Score, Heart Rate and SpO ₂			X	X	X			
Vital Sign Measurements (includes SpO ₂ via pulse oximetry)			X	X	X	X	X	
Telephone contact		X						
Pregnancy test	X ⁴		X ⁴	X ⁴	X ⁴	X ⁴	X ⁴	
MetHgb	X				X	X ⁵	X	
Hematology, Chemistry					X	X ⁵	X	

Evaluation for Symptomatic Rebound PH	X ⁶		X	X	X		
AEs/SAEs/AESIs		X	X	X	X	X	X
Drug Dispensing for Open Label Extension	X ¹		X ⁷	X ⁷	X ⁷	X ⁷	
Drug/Device Usage			X ⁸	X ⁸	X ⁸	X ⁸	X ⁸

¹ Ensure the subject has agreed to participate in both parts of the PAH-004 study by checking and initialing Part 1 & Part 2 participation in the ICF

² Subject must have completed 18 weeks of blinded treatment

³ N/A-Footer no longer applicable as of Amendment #3

⁴ Pregnancy testing to be performed at the discretion of the Investigator.

⁵ Hematology and chemistry labs and MetHgb will be performed on a yearly basis.

⁶ Assessment Symptomatic Rebound PH: all subjects will remain in the hospital or clinic under medical supervision for 1 hour after starting study drug and for 1 hour after study drug is discontinued for observation for signs and symptoms of rebound PH. Vital signs, including heart rate, respiratory rate, blood pressure, and SpO₂ will be recorded in the supine position every 15 minutes for 1 hour, and then again every 15 minutes for another hour after discontinuation of study drug. After the 1 hour observation period off study drug, if the subject's status is unchanged with respect to vital signs and symptoms and subject does not exhibit signs or symptoms of rebound PH, they will restart their blinded study drug treatment and be sent home.

⁷ One week of Open Label Drug dispensed by site at Week 0; all other drug dispensed to subject's home via home delivery every 4 weeks thereafter

⁸ Site personnel should review INOpulse use with the subjects during study visits to encourage use as close to 24 hours per day as possible. Reasons for device interruptions should also be reviewed with the subject.

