**Table 2: Change in 6MWD from Baseline to 18 Weeks**

Variables	Module	Source of Data	Baseline Definition	Variable specific derivation	Change from Baseline analysis
6MWD	Six Minute Walk Test (SMWT)	CRF	Average of two Week 2 (V2) Assessment	No, CRF data.	Yes

For open label period, Change in 6MWD from Baseline (week 2) and from week 18 will be analysed at month 4, 8 and 12.

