**Application Of Bisection Rule:**

*Step (1)* Difference between the date mentioned on the CRF and the randomization date will be calculated.

$$\text{Difference day} = \begin{cases} \text{Date of assessment} - \text{date of randomization}, & \text{Assessments prior to randomization} \\ \text{Date of assessment} - \text{date of randomization} + 1, & \text{Otherwise} \end{cases}$$

*Step (2)*

There are seven pre-assigned nominal (planned) visit days according to the protocol.

- Screening (i.e. V0),
- Baseline(Safety Baseline) ( Day 1) (i.e.V1)
- Week 2 (Efficacy Baseline) (Day 14)(i.e.V2)
- Week 6 ( Day 42) (i.e.V3)
- Week 10 (Day 70) (i.e.V4)
- Week 14 (Day 98) (i.e.V5)
- Week 18 (Day 126)(i.e.V6)We choose intervals as follows (Table 19):

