**Table 19: Visit Schedule (Part I)**

Visit	Visit Description	Target day	Range	
Visit 0	Screening	Screening	-28	0
Visit 1	Week 0	7	1	11

Visit	Visit Description	Target day	Range	
Visit 2	Week 2 #	14	12	28
Visit 3	Week 6	42	29	56
Visit 4	Week 10	70	57	84
Visit 5	Week 14	98	85	112
Visit 6	Week 18	126	113	141
Visit Y*	Every 4 Months	X	142	$[X + ((X - \text{Target day of previous visit}) / 2)]$

\*: Subsequent visit in Part II

#: Baseline for efficacy endpoints

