### Step (3)

When there are multiple assessments in a particular visit window, the following rules are applied to select one value representing the subject in summary statistics.

- When there are multiple assessments falling in a particular visit window then the one which is closest to the scheduled visit day will be chosen. For safety assessments like Laboratory and Vitals consider average of observations.
- The visit will be missing if no assessment was reported within the specified visit window around the scheduled visit day.
- If the difference between two duplicate records is more than or equal to 14 days, then the former duplicate record will be assigned to previous visit. The difference of 14 days is chosen because the difference between all the visits is 28 days. For safety assessments like Laboratory and Vitals consider average of observations.

The details of the different assessments ([Table 20](#) and [Table 21](#)) to be done at each visit during the trial as follows:

Table 20: Schedule of Assessment (Part I)

Assessment	Screening	Run-in		Blinded Treatment Period				
		Baseline (Within 28 Days of Screening) Week 0	Week 2 (± 3 Days)	Week 6 Month 1 (± 7 Days)	Week 10 Month 2 (± 7 Days)	Week 14 Month 3 (± 7 Days)	Week 18 Month 4 (± 7 Days)	EOS (Early Discontinuation)
Informed Consent	X							
Inclusion/ Exclusion	X							
Medical History	X							
Prior and Concomitant Medication	X	X	X	X	X	X	X	X
WHO Functional Class	X	X	X	X	X	X	X	X
6 Min Walk Test	X	X a	X a	X	X	X	X	X
Borg Dyspnea, Heart Rate and SpO 2	X		X	X	X	X	X	X
Vital Signs (SpO 2 via Pulse Oximetry)	X	X	X	X	X	X	X	X
Total Lung Capacity (TLC)	X b							
Spirometry Testing (and DLCO)	X c						X	X
Physical Examination	X d						X	X
Pregnancy Test	X						X	X
MetHgb	X		X	X				X

Assessment	Screening	Run-in		Blinded Treatment Period				
Hematology, Chemistry	X						X	X
NT-proBNP	X						X	
Eligibility for INOpulse (Average Daily Use ≥ 12 hr/day)			X h					
Randomization		X						
Right Heart Catheterization (RHC) (Subset of ~ 50 Subjects)		X					X	X i
Right Heart Catheterization (RHC) (all subjects not enrolled in subset)	X j							
Echocardiogram for central reading (subset of ~50 subjects)		X			X		X	X i
Echocardiogram for local Reading only (all subjects not enrolled in subset)		X						X i
Evaluation of Symptomatic Rebound pH		X k	X					

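### SAP Table 18 counts Part 2 efficacy windows from a fixed study day 126 and gives Week 52 no window; Table 19's Part 2 safety windows nest if read literally

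*SAP*

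**What the plan says.** **Efficacy windows.** SAP 5.2, Table 18, gives Part 2 Week 0 a target of day 126, Week 2 day 140, Week 16 day 238 (224-252) and Week 32 day 350 (336-364). The next and last row is "Every 4 months until EOS" (V11 onwards). Its target is marked not applicable and its day range is left to be set as appropriate. The sentence under the table reads "All efficacy analysis will follow above given study assessment window range".

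**When Part 2 starts.** The Part 2 half of Protocol Table 2 heads its first column "Week 0 If subject enters Part 2, Week 0 assessments are done at Week 18 of Part 1". The Part 1 Week 18 visit carries ±7 days. Weeks 16, 32 and 52 of Part 2 carry ±14 days.

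**What is measured and analysed.** Protocol section 11 lists "Part 2: Week 16, Week 32, and Week 52 Visits", each with a 6-minute walk test, and SAP Table 21 has the same Week 52 column. SAP 4.1 says "For open label period, Change in 6MWD from Baseline (week 2) and from week 18 will be analysed at month 4, 8 and 12". SAP 7.4.2 and 7.6.5 plan the same three time points for WHO class and Borg score.

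**Safety windows.** SAP Table 19 sits under the bisection rule. After Week 18 (days 113-141) it has one generic row, footnoted "Subsequent visit in Part II". The lower limit is 142. The upper limit is the visit's target plus half the distance back to the previous target. Step (3) averages laboratory and vital-sign values that share a window.

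**The concern.** A window table should map a visit done on schedule to that visit. Table 18 counts from randomization, but Part 2 weeks have meaning only from the subject's own open-label start. Protocol 7.2.2 defines the Part 2 secondary endpoint at 4, 8 and 12 months of therapy. A subject who starts Part 2 a week late and attends Week 16 within the permitted ±14 days can still miss the window.

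Month 12 is a named analysis time with no stated window, so someone would have to choose one later. For safety, a lower limit of 142 on every Part 2 visit would put the month 4 and month 8 vital signs into the month 12 window as well, which bisection is meant to prevent.

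At stake are the by-visit Part 2 results. Only subjects who switch from placebo contribute to the secondary endpoint, so each usable walk counts.

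**Working it through.** **1. Reproduce Table 18.** Target = 126 + 7 × Part 2 week; range = target ± window.

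| Part 2 visit | Target | Range computed | Range stated |
|---|---|---|---|
| Week 0 | 126 | 119-133 | 118-133 |
| Week 2 | 126 + 14 = 140 | 137-143 | 137-143 |
| Week 16 | 126 + 112 = 238 | 224-252 | 224-252 |
| Week 32 | 126 + 224 = 350 | 336-364 | 336-364 |
| Week 52 | 126 + 364 = 490 | 476-504 | none |

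The fixed anchor is confirmed. The one-day difference at Week 0 also appears for Week 18 in Table 17.

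**2. Where on-schedule walks can fall.** Let *s* be the Week 18 offset (-7 to +7) and *v* the Part 2 visit offset from the subject's own start (-14 to +14).

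- Week 16: 238 ± 21 = days 217-259. Outside Table 18: 217-223 and 253-259.
- Week 32: 350 ± 21 = days 329-371. Outside: 329-335 and 365-371.
- Week 52: 490 ± 21 = days 469-511. No range to compare with.

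**3. How many fall outside.** A walk is outside when |*s* + *v*| > 14. For a given *s*, exactly |*s*| of the 29 values of *v* meet this. The documents give no distribution of offsets, so these are assumptions, with *s* and *v* independent:

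- *Uniform:* 2 × (1 + 2 + … + 7) = 56 of 15 × 29 = 435 combinations, or 12.9%. With the stated start range 118-133 it is 64/464 = 13.8%.
- *Uniform, Week 18 within ±3 days:* 2 × (1 + 2 + 3) = 12 of 7 × 29 = 203, or about 6%.
- *Triangular* (weights 8 - |*s*| and 15 - |*v*|): the sum over *s* = 1 to 7 of (8 - *s*) × *s* × (*s* + 1) is 14 + 36 + 60 + 80 + 90 + 84 + 56 = 420, out of 64 × 225 = 14,400, or 2.9%.
- *Every subject starts on day 126:* 0%.
- *Subject starting on day 119 or 133:* 7 of 29 permitted days, or 24%.

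**4. Table 19 read literally.** Lower limit 142 throughout; upper limit X + (X - previous target)/2:

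- Week 16: 238 + (238 - 126)/2 = 294, so 142-294 (287 if Part 2 Week 2, day 140, is taken as the previous visit).
- Week 32: 350 + (350 - 238)/2 = 406, so 142-406.
- Week 52: 490 + (490 - 350)/2 = 560, so 142-560.

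Each window contains the ones before it. Midpoints between adjacent targets are (126 + 238)/2 = 182, (238 + 350)/2 = 294 and (350 + 490)/2 = 420. The upper-limit formula also misses the midpoint where spacing changes: 406 against 420 between Weeks 32 and 52.

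**The case against.** Several points on the other side have force.

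- **The origin is inferred.** The protocol does not say in words that the ±14 days run from the subject's actual Part 2 start. That stands as a caveat. But Part 2 Week 0 is done at the subject's Week 18 visit and the endpoint is months of therapy, so no other origin fits as well.
- **Month 12 walks are not shown to be lost.** A reader might take the row after Week 32 as 16 weeks later, at 350 + 112 = day 462 (448-476), and infer that nearly all Week 52 walks are excluded. The documents do not support this. Table 18 states no target for that row. Following rows labelled Month 4 and Month 8, it is more naturally Month 12, day 490. The defect is an unspecified window.
- **Out-of-window does not expressly mean missing for efficacy.** The sentence "The visit will be missing if no assessment was reported within the specified visit window around the scheduled visit day" is printed in Step (3) of the safety mapping. For efficacy the SAP says only that analyses follow the Table 18 ranges. Walks outside them have no stated place, but deletion is not spelled out.
- **Day 142 may be loose drafting.** It is 141 + 1, the natural start of the first interval after Week 18. That is probably what was meant, but the footnote extends the row to every later Part 2 visit and supplies no other lower limit.
- **No diluted vital-sign result can be claimed.** A reader might infer that averaging across nested windows would shrink a late vital-sign change. SAP 7.7 has no vital-sign subsection and SAP 9.0 replicates only the adverse-event tables for Part 2, so no specified analysis would show it. Part 2 laboratory tests are at Week 52, then yearly and at exit, so they would pool little.

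**Conclusion.** The point holds and is minor. Table 18's fixed day 126 leaves some on-schedule Week 16 and Week 32 walks outside the binding windows. The share depends on assumed visit offsets: 12.9% if uniform, 2.9% if triangular, none if every subject starts on day 126. The missing Week 52 window needs no such assumption. The nesting in Table 19 follows from its literal wording and conflicts with the bisection rule it implements.

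The effect is confined to the Part 2 walk-distance endpoint, which SAP 9.0 makes descriptive, the open-label WHO class and Borg analyses, and any by-visit Part 2 safety summary. Part 1 efficacy inference does not use these windows, and neither does Part 2 adverse-event or serious-adverse-event incidence. The documents do not support wholesale loss of month 12 walks or a quantified masking of a safety signal.

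**What to change.** 1. Define Part 2 Day 1 as each subject's first open-label day and count Part 2 visits from it: Week 16 = 1 + 112 = Day 113 (99-127), Week 32 = 1 + 224 = Day 225 (211-239), Week 52 = 1 + 364 = Day 365 (351-379), each ±14 days.
2. Add the Week 52 row to Table 18, so that the every-4-months row starts after it.
3. In Table 19, start each Part 2 safety window the day after the previous one ends, with limits at midpoints between adjacent targets: Days 57, 169 and 295 on the Part 2 scale, from (1 + 113)/2, (113 + 225)/2 and (225 + 365)/2. Align the end of the Week 18 window (now day 141) with the first of these; no Part 2 vital signs are scheduled in between.
4. State for efficacy how an out-of-window walk is handled.

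The cost is edits to two SAP tables, one added sentence and the matching programming. No new visits or data are needed.
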